Primary Objective:

To assess the concordance of temperature obtained continuously by a thermal imaging camera with that obtained by an axillary contact thermometer.

Secondary Objectives:

1. To describe the sociodemographic (age and gender) and clinical characteristics (HTN, DM, DL, reason for ICU admission, SAPS3) of the study population.
2. To study the diagnostic test validity of the thermal imaging camera for fever and hypothermia. Fever is defined as an axillary temperature of $\geq 37.5^{\circ}\text{C}$, and hypothermia is defined as an axillary temperature $< 34.2^{\circ}\text{C}$.
3. To determine the time difference until fever detection between the SF-HANDHELD-80TA05 thermal imaging camera or similar, and temperature measurement through the usual nursing practice following standard protocols in critical patients.
4. To describe the continuous thermal curve patterns taken by the thermal imaging camera in patients with the following pathologies: altered level of consciousness, acute coronary syndrome, cardiac rhythm disturbances, cardiac arrest, heart failure cardiogenic shock, hypovolemic shock, sepsis/septic shock, shock of other etiology, respiratory failure, renal failure, metabolic disorders, intoxications, trauma, postoperative monitoring and surveillance, non-surgical procedure monitoring and surveillance, and others. Thermal curves will be obtained in at least 20 patients per pathology.

5. To describe the continuous thermal curve patterns taken by the thermal imaging camera in patients with infectious complications in two cases: patients with infection upon admission and patients who develop infection during admission. Thermal curves will be obtained in at least 20 patients in each case.
6. To determine the adequacy of regional thermal measurement by reviewing the complete thermal image obtained by the SF-HANDHELD-80TA05 or similar camera

Materials and Methods

Design:

This is a single-center, observational, descriptive, longitudinal, and prospective study to investigate the concordance between temperatures obtained by the thermal imaging camera and axillary temperatures.

Scope and Study Population:

The study will be conducted on all patients admitted to the ICU rooms at HLA Moncloa University Hospital equipped with an infrared camera for continuous measurement of skin temperature.

Inclusion Criteria:

- Patients admitted to the ICU in a room with a thermal imaging camera
- Aged 18 years and above

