- Patients who provide voluntary consent to participate in the study (Annex 2). If the participant is not in full physical or intellectual capacity to provide their signature in the informed consent, the responsible investigator will seek consent from their direct family member or the legally designated person to make decisions on their behalf regarding health matters. This measure is adopted to ensure the participant's rights are respected and the integrity of the consent process is maintained, even in situations where their decision-making capacity may be compromised.

Exclusion Criteria:

Patients from whom information from the thermal imaging camera cannot be obtained due to technical reasons.

Sample Size:

To determine the degree of concordance between the temperature recorded by the thermal camera and axillary temperature, a minimum of 224 pairs of data (224 temperature records by thermal camera vs. 224 axillary temperature records) will be required to estimate an Intraclass

Correlation Coefficient (expected to be 0.8 or higher) with an estimation error of +- 0.05 points, a confidence level of 95%, and anticipating a 10% loss.

Data Collection:

Temperature measurements will be autonomously recorded by the SF-HANDHELD-80TA05 thermal imaging camera, or another with similar characteristics, which provides temperature values every second, thermal images, bed number, date, and time.

The rest of the variables needed for the study will be manually collected by the researchers or through the clinical information system (CIS) "Innovian" and included in a study-dedicated database hosted on the hospital intranet.

Finally, all data will be collected in a pseudonymized manner. For this purpose, two databases will be constructed. One will contain personal data associated with a code (one for each patient), which will be safeguarded by the investigator. The second database will contain the associated clinical data. In the case of images generated by thermal cameras, these will also be pseudonymized, generating images with the aforementioned association code. These coded images will be sent to the Computing Center of the European University of Madrid for the creation of temperature patterns (secondary objectives 4 and 5) and for the adequacy of regional thermal measurement (secondary objective 6).

Standard Practice in Peripheral Temperature Measurement in Our Unit

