The standard practice for peripheral temperature measurement in the ICU at HLA Moncloa University Hospital is not formally documented but adheres to recommendations for monitoring temperature in critically ill patients. Peripheral temperature is obtained using a contact thermometer in the axilla every 8 hours or whenever thermal disturbances are suspected by healthcare personnel (both medical and nursing staff).

Axillary temperature measurement through standard practice will be repeated every 8 hours and collected in triplicate to establish an average used for assessing concordance at that point and so forth until reaching the 224 measurements needed to complete the primary objective of the study. If, during the 8-hour collection, there is a difference of more than 15% between the first 3 measurements, a fourth measurement will be taken, and only the average of the three most similar measurements will be used for concordance. If all four measurements are different, a fifth measurement will be taken, and so on until three measurements considered similar are obtained.

Definitions of Thermal Disturbances and Infectious Complications:

- Fever: Defined as a central temperature (rectal, esophageal, vesical, or tympanic) $\geq 38.3^{\circ}\text{C}$. Peripheral temperature (cutaneous or axillary) is 0.6 to 1°C lower than central temperature; therefore, for this study, we will consider a peripheral temperature $\geq 37.5^{\circ}\text{C}$ as a fever.
- Hypothermia: Defined as a central temperature $< 35^{\circ}\text{C}$ or peripheral temperature $< 34.2^{\circ}\text{C}$.
- Infectious Complications: Will include both patients admitted to the ICU due to an infection (pre-admission infection) and patients who develop an infection during their stay in the ICU (infection during admission). Identification and diagnosis of either type of infection will be

carried out by the attending physician following established clinical practice recommendations and guidelines in each specific case. The task of the researchers will be limited to reviewing the patient's medical history and collecting data.

Temporal Differences in Fever Detection:

The time of fever detection will be identified for each measurement method (standard practice vs. thermal imaging camera), and the temporal difference in minutes between them will be determined.

Creation of Temperature Patterns:

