Continuous temperature data (every second) offered by thermal cameras will be represented by 24-hour thermal curves and classified automatically based on patterns and patient characteristics using unsupervised machine learning algorithms such as clustering. For this purpose, the data will be physically and securely sent to the Computing Center of the European University of Madrid.

Adequacy of Regional Thermal Measurement:

Thermal cameras SF-HANDHELD-80TA05 or similar perform a scan across the entire thermal image to extract the point of maximum temperature found. It is deemed necessary for the study to visually check the thermal images obtained to verify the adequacy of temperature measurement—ensuring that the temperature is being obtained from the patient and not from any other high-temperature element, such as healthcare personnel or electronic devices (mobile phones, respirators, pumps, etc.). A direct visual check of a sample of thermal images will be performed by the researchers, and all thermal images will be physically and securely sent to the Computing Center of the European University of Madrid for automatic classification using convolutional image recognition algorithms (machine learning) to identify whether the temperature is obtained from the patient or any other element.

Interventions and Procedures:

1. All patients admitted to the ICU in a room with a thermal imaging camera will be considered potential candidates for inclusion in the study and will be verbally informed and provided with patient information sheets about the study, requesting their signature on the informed consent form for participation.
2. If they agree to participate, compliance with inclusion and exclusion criteria will be confirmed.
3. Patients will receive treatments according to the center's usual clinical practice and the criteria of their attending physician based on the patient's characteristics in each specific case.
4. The thermal imaging camera will automatically record temperature readings every second and capture a thermal image. The information will be recorded in real-time on

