- Time to Fever Development

Statistical Analysis Plan

The degree of agreement between temperature measurements recorded with the thermal camera and measurements taken with the axillary contact thermometer will be assessed, as these are quantitative variables, through the intraclass correlation coefficient. Qualitative variables will be summarized based on absolute and relative frequency (n and %), while normally distributed quantitative variables will be described using mean \pm standard deviation (SD), or if not normally distributed, using median and interquartile range. Normality will be determined using the Kolmogorov-Smirnov test.

The validity of the thermal camera as a diagnostic test for fever and hypothermia will be calculated based on sensitivity and specificity, as well as Positive Predictive Value (PPV) and Negative Predictive Value (NPV). Considering fever is defined as $\geq 37.5^{\circ}\text{C}$ in axillary temperature, and hypothermia as $<34.2^{\circ}\text{C}$ in axillary temperature.

Limitations

This is a single-center study; other units may have different protocols for monitoring, managing, and treating fever, or admit patients with different baseline characteristics than those in this sample, so the conclusions of this study may not be applicable to other services.

Ethical and Legal Aspects

This study will be conducted in accordance with current legislation. All participating researchers will adhere to strict confidentiality in accessing, collecting, and processing data in

the databases, and commit to strict compliance with relevant laws: Law 41/2002, of November 14, which regulates patient autonomy and rights and obligations regarding clinical information and documentation, Organic Law 3/2018, on the protection of personal data and the guarantee of digital rights, and Regulation (EU) 2016/679 of the European Parliament and of the Council of April 27, 2016, on the protection of individuals concerning the processing of personal data and on the free movement of such data, repealing Directive 95/46/EC (General Data Protection Regulation).

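### One fever and one hypothermia cut-off are shared by skin and axilla, so sensitivity and specificity at that value confound a camera offset with its ability to discriminate.

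*Protocol*

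**What the plan says.** - **Accuracy measures.** The Statistical Analysis Plan section of the protocol states: "The validity of the thermal camera as a diagnostic test for fever and hypothermia will be calculated based on sensitivity and specificity", and adds PPV and NPV. It lists no other diagnostic measure.
- **Reference standard.** The same section, like secondary objective 2, defines fever and hypothermia on the axillary reading (37.5 °C or above; "hypothermia as $<34.2^{\circ}\text{C}$ in axillary temperature"). Neither place states when a camera reading counts as positive.
- **Shared cut-offs.** Definitions of Thermal Disturbances and Infectious Complications starts from central values (38.3 °C for fever, 35 °C for hypothermia). It states: "Peripheral temperature (cutaneous or axillary) is 0.6 to 1°C lower than central temperature". From this it adopts 37.5 °C and 34.2 °C for any peripheral temperature.
- **What the camera reads.** Scope and Study Population describes an "infrared camera for continuous measurement of skin temperature". Adequacy of Regional Thermal Measurement explains that the cameras "perform a scan across the entire thermal image to extract the point of maximum temperature found", and accepts that this point may belong to staff or equipment and not to the patient.
- **Expected agreement.** Sample Size expects an intraclass correlation of at least 0.8, without naming the form of the coefficient.

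**The concern.** The definitions place skin and axillary temperature on one scale, with one distance from central temperature. The camera's value is a different quantity, the maximum of a remote image, and nothing in the protocol shows that it lies on the axillary scale. Whether it does is the primary question of the study.

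Sensitivity and specificity need a positivity rule for the camera, and the shared value is the only one stated. At a single fixed cut-off, two properties act together: how well the camera ranks feverish above non-feverish readings (discrimination), and how far its scale is shifted (calibration). A camera that ranks well but reads cool would show low sensitivity. One that ranks less well but reads warm would show high sensitivity. For hypothermia the direction reverses, and a warm-reading camera loses sensitivity. With only the four planned measures, a reader could not tell a correctable shift from a camera that cannot detect fever. Secondary objective 3, time to fever detection by each method, also needs a camera fever value and has only the same one to draw on.

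**Working it through.** **1. The plan's own figures.**
- Cut-offs: 38.3 − 0.8 = 37.5 and 35 − 0.8 = 34.2. Here 0.8 is the midpoint of the stated gap of 0.6 to 1 °C. One shift serves skin and axilla alike.
- Sample size: the Bonett precision formula, n = 8z²(1−ρ)²(1+(k−1)ρ)² / [k(k−1)w²] + 1, with z = 1.96, ρ = 0.8, k = 2 and full width w = 0.10, gives 200.1, rounded up to 201. Then 201/0.9 = 223.3, rounded up to 224, as stated. The protocol gives no accuracy target and no expected camera offset.

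**2. Assumptions for the illustration (not in the documents).** Axillary temperature A ~ N(36.8, 0.7). Camera C = A + d + e, with constant offset d and random error e ~ N(0, 0.3). Both are cut at 37.5 °C.

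**3. How large an offset fits the expected ICC.** If the ICC of 0.8 means absolute agreement:

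ICC = 2·SD² / [SD² + (SD² + error SD²) + d²] = 0.98 / (0.49 + 0.58 + d²).

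Setting this to 0.8 gives d² = 0.98/0.8 − 1.07 = 0.155, so d is about ±0.39 °C. A consistency ICC leaves d out and sets no limit.

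**4. Fever accuracy at the shared cut-off.** Sensitivity = P(C ≥ 37.5 | A ≥ 37.5) and specificity = P(C < 37.5 | A < 37.5), from the bivariate normal distribution:

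| Offset (°C) | Sensitivity | Specificity | Absolute-agreement ICC |
|---|---|---|---|
| −0.39 | 0.45 | 0.99 | 0.80 |
| −0.20 | 0.63 | 0.98 | 0.88 |
| 0 | 0.80 | 0.94 | 0.92 |
| +0.20 | 0.92 | 0.87 | 0.88 |
| +0.39 | 0.98 | 0.78 | 0.80 |

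The AUC is 0.96 in every row, because adding a constant does not change the ranking. A cut-off at the maximum Youden index, which moves with the offset, gives about 0.92/0.87 in every row.

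**5. A second model.** Assume axillary mean 36.7 °C, equal SDs of 0.7 °C and correlation 0.9. Then ICC = 2(0.9)(0.49)/(0.98 + d²) = 0.8 gives d² = 0.1225 and d = ±0.35 °C. Sensitivity/specificity are 36%/99.5% at −0.35, 71%/96% at zero and 94%/84% at +0.35, with the AUC at 0.959 throughout. With correlation 0.8 an absolute-agreement ICC of 0.8 leaves no room for an offset; sensitivity/specificity are then 58.8%/94.0%.

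**6. Expected events in 224 pairs under the assumptions of step 2.**
- Fever: P(Z ≥ (37.5 − 36.8)/0.7) = P(Z ≥ 1) = 0.159, about 36 pairs.
- Hypothermia: P(Z < (34.2 − 36.8)/0.7) = P(Z < −3.71), about 0.0001, or about 0.02 pairs. Real ICU temperatures may have heavier tails, but these assumptions give no support for a hypothermia ROC curve.

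**The case against.** **The analysis section fixes only the reference.** A reader might infer that it prescribes 37.5 °C and 34.2 °C for the camera. It does not: both values are given there for the axilla, and a camera threshold could be set in a separate SAP. This stands. The point rests on the definitions section, which does state a value for skin temperature and gives no reason why it should equal the axillary one.

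**The cut-offs were not derived for the axilla.** That is correct. They come from central temperature, for skin and axilla together. The weakness is treating the two as interchangeable, not borrowing an axillary value.

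**The offset may be small.** A reader might infer that the planned results will mostly measure the offset. The documents give neither its size nor its direction, and near zero the accuracy depends on the random error and the spread of temperatures. Offsets of ±0.5 or ±1.0 °C would give more striking figures, but under the first model they imply an absolute-agreement ICC of 0.74 or 0.47, below what the protocol expects. They are not a fair measure of size unless the ICC is of the consistency form.

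**The same-value comparison is legitimate.** The hypothesis is agreement with the axillary thermometer. Whether the camera classifies patients as that thermometer does, at the same number, is a proper question, and for it an offset is a real error. This stands, so that result should be kept. It does not remove the need to show discrimination separately, because objective 2 asks about the camera's validity as a diagnostic test.

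**Conclusion.** The point holds in this form: the protocol puts skin and axillary readings on one scale without support and states no other camera positivity rule. It plans only measures that depend on that value, so calibration and discrimination cannot be separated.

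Under the first model, offsets within ±0.39 °C move fever sensitivity between 0.45 and 0.98 and specificity between 0.99 and 0.78, with discrimination unchanged. The second model gives 36% to 94% and 99.5% to 84% within ±0.35 °C. Both ranges rest on assumed distributions and on reading the ICC as absolute agreement.

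The documents do not show that an offset exists, that it would dominate the results, or that the same-value analysis is wrong. The effect on hypothermia accuracy is not quantified here beyond its direction.

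**What to change.** 1. Keep the axillary values as the reference definitions, and keep sensitivity, specificity, PPV and NPV at the same value, labelled as the interchangeability result.
2. For fever, add the mean camera-minus-axilla difference, the ROC curve and the AUC, with confidence intervals that allow for repeated pairs per patient.
3. For fever, also report sensitivity and specificity at a camera cut-off chosen by a pre-stated statistical rule, such as the maximum Youden index. Correct for optimism at patient level (cross-validation or bootstrap) and label the result exploratory.
4. For hypothermia, do the same only if enough events occur, with the minimum number stated in advance. Otherwise report descriptively.
5. State in the definitions section that applying one value to skin and axilla is a working assumption that the study will examine.

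This changes the analysis wording and uses the same paired data. The cost is that a cut-off derived from these data needs later confirmation, and that its precision will be limited by the number of fever pairs and of distinct patients. No clinical threshold is proposed.
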